3.2 Exclusion Criteria

BMSM who meet any of the following criteria will be excluded from this study:

- Any reactive or positive HIV test at Screening, even if subsequent testing indicates that the person is HIV-uninfected
- Transgender
- Active or chronic hepatitis B infection (as evidenced by HBsAg, HbsAb, and HbcAb testing)
- Planning to move out of the area or to travel for more than 3 months during the study follow-up period
- Unwilling to adhere to study procedures
- Current participation in any research study via self-report (however, strictly non-HIV centered observational studies are not exclusionary)
- Previous participation in an HIV vaccine study is exclusionary unless documented evidence of enrollment into a placebo arm
- Use of ARV drugs (PrEP or PEP) in the last 60 days
- Prior history of a gastrectomy, colostomy, ileostomy, or any other procedure altering the gastrointestinal tract or drug absorption (provided by self-report, or obtained from medical history or records)
- Receipt of prohibited medications: interleukin therapy, medications with significant nephrotoxic potential (including but not limited to amphotericin B, aminoglycosides, cidofovir, foscarnet and systemic chemotherapy), and medications that may inhibit or compete for elimination via active renal tubular secretion (including but not limited to probenecid) (provided by self-report, or obtained from medical history or medical records)
- Any condition, that in the opinion of study staff, would make participation in the study unsafe, or interfere with achieving the study objective

Note: A maximum of 45 days are allowed between enrollment and the time of the first screening laboratory draw.

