Note: Indication and Usage for Pre-exposure Prophylaxis will be reviewed with participants as part of a comprehensive package of risk reduction services. In general, sites must refer to the CDC interim guidelines for PrEP administration

(http://www.cdc.gov/hiv/prep/pdf/PrEPfactsheet.pdf) and to the guidelines for PrEP Indication (https://www.truvadapreprems.com/#). A manual will be created for all sites to follow when introducing PrEP to participants based on safety and efficacy language found in the ICF under "Study Purpose".

If initiating or on PrEP:

- Assess participant's initial readiness for PrEP adherence (only if initiating)
- Self-reported study product adherence assessment
- Study product supply
- Autonomy supportive adherence counseling
- o PrEP Adherence Self-Regulation Questionnaire (participant self-administered)
- PrEP adherence goal setting
- C4 including:
 - Care Coordination Measurement Tool (recorded by providers)
 - Health Care Climate Questionnaire (participant self-administered)

Clinical Evaluations/ Procedures

- Interim medical history including concomitant medications
- Urine collection
- Blood collection

Laboratory Evaluations/ Procedures

- HIV testing per algorithm in the SSP Manual
- Renal function tests (BUN, creatinine at Week 4 only)
- Calculated creatinine clearance (Week 4 only)
- Plasma storage for Pharmacology testing (Week 8 only)**
- Lysed PBMC storage for Pharmacology testing (Week 8 only)**
- DBS storage for possible Pharmacology testing (Week 8 only)**
- Urine storage for substance use testing

• Plasma storage for QC / Virology testing

*Conduct a visit consisting of Week 4 procedures 4 weeks after initiating PrEP, or 4 weeks after a participant re-initiates PrEP.

**Plasma and DBS samples will be processed and stored for all participants; testing may be limited to a subset of these samples. Lysed PBMC samples will be processed and stored only for participants who report that they used PrEP within 60 days of sample collection.

Note: Any participant who has not taken PrEP in the past 60 days and wishes to start PrEP at this visit must first be confirmed to be eligible according to the Screening Visit parameters.

5.5 Week 13

Administrative and Behavioral Evaluations/ Procedures

- Review and update locator information
- Social Harms and AE Assessment
- Behavioral and Psychosocial Risk Survey (ACASI)
- HIV/STI behavioral counseling (pre- and post-test), including risk-reduction counseling
- PrEP discussion

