- Offer condoms and other prevention supplies

Note: Indication and Usage for Pre-exposure Prophylaxis will be reviewed with participants as part of a comprehensive package of risk reduction services. In general, sites must refer to the CDC interim guidelines for PrEP administration

(http://www.cdc.gov/hiv/prep/pdf/PrEPfactsheet.pdf) and to the guidelines for PrEP Indication (https://www.truvadapreprems.com/#). A manual will be created for all sites to follow when introducing PrEP to participants based on safety and efficacy language found in the ICF under "Study Purpose".

If initiating or on PrEP:

- Assess participant's initial readiness for PrEP adherence (only if initiating)
- Self-reported study product adherence assessment
- Study product supply
- Autonomy supportive adherence counseling
- PrEP Adherence Self-Regulation Questionnaire (participant self-administered)
- PrEP adherence goal setting
- C4 including:
 - C4 Case Conference (by staff preferably prior to the Week 13 visit)
 - Health Care Climate Questionnaire (participant self-administered)
 - Client Perception of Coordination Questionnaire (participant self-administered)
 - Care Coordination Measurement Tool (recorded by providers)

Clinical Evaluations/ Procedures

- Interim medical history including concomitant medications
- Symptom-driven physical exam

- Blood collection
- Urine collection

Laboratory Evaluations/ Procedures

- HIV testing per algorithm in the SSP Manual
- Renal function tests (BUN, creatinine)
- Calculated creatinine clearance
- Urine dipstick for protein and glucose
- Urine storage for substance use testing
- Plasma storage for QC / Virology testing

Note: Any participant who has not taken PrEP in the past 60 days and wishes to start or restart PrEP at this visit must first be confirmed to be eligible according to the Screening Visit parameters. This does not have to be performed at a separate "interim" visit. Screening procedures can be repeated at any scheduled study visit if they needed to confirm eligibility for PrEP administration. All assessments to determine eligibility for PrEP initiation (including laboratory testing) must have been conducted within the previous 45 days.

5.6 Weeks 26, 39 and 52

Administrative and Behavioral Evaluations/ Procedures

- Review and update locator information
- Social Harms and AE Assessment
- Behavioral and Psychosocial Risk Survey (ACASI)
- Qualitative Interview (Week 52 only)
- Adherence goal setting (except Week 52)

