- Hepatitis testing (HbsAg, HbSAb, HbcoreAb)**
- Plasma storage for Pharmacology testing (Weeks 26 and 52 only)***
- Lysed PBMC storage for Pharmacology testing (Weeks 26 and 52 only)***
- DBS storage for possible Pharmacology testing (Weeks 26 and 52 only)***
- Urine storage for QA of substance use testing
- Plasma storage for QC / Virology testing

*For participants who decide to initiate PrEP at or after Week 48, partnerships will be established as applicable with community partners in order to provide adequate clinical care and follow-up.

**Hepatitis testing should be repeated at Week 52 for participants who were non-immune at the Screening visit, declined HBV vaccination, or were not diagnosed with HBV infection during the study.
***Plasma and DBS samples will be processed and stored for all participants; testing may be limited to a subset of these samples. Lysed PBMC samples will be processed and stored only for participants who report that they used PrEP within 60 days of sample collection.

Note 1: Any participant who has not taken PrEP in the past 60 days and wishes to start or restart PrEP at Week 26, Week 39 or any other visit up to Week 48 must first be confirmed to be eligible according to the Screening Visit parameters. This does not have to be performed at a separate "interim" visit. Screening procedures can be repeated at any scheduled study visit if they needed to confirm eligibility for PrEP administration. All assessments to determine eligibility for PrEP initiation (including laboratory testing) must have been conducted within the previous 45 days.

Note 2: Staff Focus Groups will begin after all participants have completed the study.

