7.3 Data Analysis

7.3.1 Primary Analyses

- To assess initiation and adherence of daily PrEP among BMSM who are offered PrEP. PrEP acceptability will be assessed by the acceptance/refusal rate of PrEP. PrEP initiation will be measured by time-to-PrEP initiation. The measure of initiation can be a participant's use of PrEP at any point in the study. Acceptance and refusal rates will be calculated, with 95% exact or normally approximated binomial confidence intervals. Acceptance and refusal rates will also be calculated by age, education, site, and risk practices. In addition, to identify correlates associated with refusal, we will use backward stepwise multivariate logistic regression models to examine statistically significant factors. Predictiveness of associated factors will be summarized by respected ROC curves. Kaplan-Meier plots will be used to characterize time to PrEP initiation, overall and by age, education, and risk group.
- To assess adherence and persistence to PrEP among participants in the demonstration project. • PrEP persistence time is defined as the time from PrEP start to PrEP discontinuation. A PrEP discontinuation is considered to have occurred if a participant self-reported via ACASI to miss the PrEP doses for 30 or more consecutive days, for reasons other than a medication hold instituted by a clinician.. Kaplan-Meier plots will be used to characterize time to first discontinuation, as well as time to restarting PrEP among discontinuers, both overall and by age, education, and risk group. Among those continuing on treatment, we will consider the so-called medication possession ratio, defined as the number of tablets dispensed divided by the number of days between visits, a measure that performed best as an indicator of drug exposure in the iPrEx study. Adherence patterns of interest (e.g., intermittent use only before planned exposures) will also be assessed by self-report, and their prevalence characterized by reporting period. Tablet-taking practices will also be evaluated by drug detection rates in biological samples. Concordance between quantitative adherence measures based on self-report and pharmacological measures will be assessed using Bland-Altman plots; concordance of binary measures of drug detection will be assessed using the Kappa statistic. PrEP persistence times will be analyzed by multiplicative Andersen-Gill counting processes models.

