- ¹² Renal function tests (BUN and creatinine) and creatinine clearance are only performed at Week 52 for participants who report that they have used PrEP in the previous 60 days.
- ¹³ Repeat dipstick urine testing at enrollment if result from the Screening visit is > trace for either protein or glucose.
- ¹⁴ Plasma and lysed PBMC will be collected for ARV drug testing. Plasma may also be tested using a high-throughput multi-drug ARV drug screen (qualitative testing). DBS will be collected for possible ARV drug testing, using assays that are in development. Plasma and DBS samples will be processed and stored for all participants; testing may be limited to a subset of these samples. Lysed PBMC samples will be processed and stored only for participants who report that they used PrEP within 60 days of sample collection.

¹⁵ Week 8 only.

¹⁶ Weeks 26 and 52 only.

- NOTE 1: If any participant wishes to start or restart PrEP after enrollment, eligibility must be confirmed using all Screening criteria. If assessments performed at the Screening visit occurred more than 45 days earlier, all of these assessments, including laboratory tests, must be repeated (see Section 5).
- NOTE 2: For participants who decide to initiate PrEP at or after Week 48, partnerships will be established as applicable with community partners in order to provide adequate clinical care and follow-up.

⁵ Weeks 26 and 39 only.

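### Appendix IA NOTE 1 omits the 60-day condition that Section 5 puts on PrEP eligibility re-checks and, taken literally, refuses new supply to men restarting after a short gap

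*Protocol*

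**What the plan says.** Four places in the protocol bear on who may be given PrEP after enrollment.

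- **Appendix IA, NOTE 1**, first sentence: "If any participant wishes to start or restart PrEP after enrollment, eligibility must be confirmed using all Screening criteria". Second sentence: "If assessments performed at the Screening visit occurred more than 45 days earlier, all of these assessments, including laboratory tests, must be repeated". A pointer to Section 5 closes this second sentence.
- **Section 5 notes.** Section 5.4 (Weeks 4 and 8): "Any participant who has not taken PrEP in the past 60 days and wishes to start PrEP at this visit must first be confirmed". Section 5.5 (Week 13) opens: "Any participant who has not taken PrEP in the past 60 days and wishes to start or restart PrEP at this visit". Section 5.6 opens the first of its two numbered notes with: "Any participant who has not taken PrEP in the past 60 days and wishes to start or restart PrEP at Week 26, Week 39", and extends this to any other visit up to Week 48. The 5.4 note speaks of starting only; the other two speak of starting or restarting.
- **Section 3.2** lists as an exclusion: "Use of ARV drugs (PrEP or PEP) in the last 60 days". It makes no exception for PrEP supplied by the study.
- **Section 7.3.1** counts a discontinuation when a man reports by ACASI that he did "miss the PrEP doses for 30 or more consecutive days, for reasons other than a medication hold instituted by a clinician". It plans Kaplan-Meier plots of time to first discontinuation, "as well as time to restarting PrEP among discontinuers, both overall and by age, education, and risk group".

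The protocol expects restarts. Section 1.2.1 has PrEP discussed at every visit with the choice to take it up, carry on, stop or abstain, and footnote 1 of Appendix IA schedules a Week 4 type visit after re-initiation.

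**The concern.** The two rules differ in scope. Section 5 ties the re-check to 60 days off drug, and NOTE 1 ties it to nothing. The difference matters because the Screening criteria include the 60-day ARV exclusion. Under Section 5 the threshold and the exclusion fit together: a man who needs the re-check has, by definition, already cleared that item. Under NOTE 1 a man who stopped three weeks ago must be re-checked and must fail, because his own study drug disqualifies him.

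At stake is a man's access to drug when he asks to resume. Two sites could also treat the same request differently, each able to cite the protocol. Because time to restart is a planned analysis, a site's choice of rule could also show up in that curve.

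**Working it through.** No sample size or error rate is involved. The check sets the rules side by side and does some day counting.

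**Step 1. What each rule gives, by time since last dose.**

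| Time since last PrEP | Sections 5.5 and 5.6 | NOTE 1 with the 3.2 item applied | NOTE 1 with the 3.2 item set aside |
|---|---|---|---|
| Never taken | Re-check; 3.2 item met | Same | Same |
| Within 60 days | No re-check stated | Re-check; 3.2 item fails; no supply | Re-check; Screening assessments over 45 days old repeated |
| More than 60 days | Re-check; 3.2 item met | Same | Same |

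The rules agree for first starts and for long gaps. They conflict only for gaps within 60 days.

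**Step 2. Weeks 4 and 8.** The Section 5.4 note does not mention restarting, so NOTE 1 is the only explicit restart rule at these visits. At nominal timing Week 8 is 8 × 7 = 56 days after enrollment, which is less than 60. Any man restarting study PrEP at the scheduled Week 4 or Week 8 visit is therefore within 60 days of his last dose and falls in the conflicting row.

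**Step 3. Repeat testing if the 3.2 item is set aside.** The minimum age of the Screening assessments is the time since enrollment:

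- Week 8: 8 × 7 = 56 days
- Week 13: 13 × 7 = 91 days
- Week 39: 39 × 7 = 273 days

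All exceed 45, so NOTE 1's second sentence calls for every Screening assessment to be repeated. CBC, hepatic function and hepatitis B tests are not routinely scheduled at Weeks 13 or 39 in Appendix IA. These are at least three test groups that a man restarting after a short gap would need under NOTE 1 and that Section 5 does not ask of him.

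**Step 4. Overlap with the restart analysis.** A discontinuation needs at least 30 missed days, and the 3.2 item looks back 60 days. The overlap is 60 − 30 = 30 days: restarts from day 30 to day 60 after the last dose count in the analysis and also fall in the conflicting row.

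**Step 5. Whether NOTE 1 reaches those restarts.** It governs eligibility to be given drug, whereas Section 7.3.1 judges dosing by ACASI self-report. From Week 13, scheduled supply visits are 13 × 7 = 91 days apart. A 30-day gap can begin and end between two of them, and a man with tablets left can resume without asking the site. NOTE 1 acts only on restarts that need new supply, and the protocol gives no figure for that share.

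**Step 6. The pool.** The 33% to 67% acceptance range in Section 7.2 gives 225 × 0.33 = 74 to 225 × 0.67 = 151 initiators. Restarters come from this group. How many would stop for 30 days or more and then seek new supply within 60 days of the last dose is not given.

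**The case against.** The strongest reply is that no site would apply NOTE 1 this way. Section 5.0 describes Appendix I as an overview and leaves standardization across sites to the study-specific procedures manual, which is not shown. NOTE 1 itself points to Section 5, and Section 10.3 names roles to settle eligibility questions consistently. Equal literalism would let the Section 3.2 exclusion for current research participation bar every start after enrollment. Section 5 also never says outright that men with shorter gaps need no check; that is inferred.

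Much of this stands. The bar is almost certainly unintended, many sites would probably follow Section 5, and actual divergence between sites is not shown. It does not remove the conflict. The pointer to Section 5 sits on the sentence about assessments over 45 days old and does not narrow the first sentence. The inference about shorter gaps is a safe one, because the 60-day condition in Section 5 would otherwise do nothing. Section 10.5 requires full compliance with the protocol, and Section 10.4 has monitors assess adherence to it. A site that supplies drug under Section 5 departs from NOTE 1 as written.

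A reader might also infer that NOTE 1 blocks resumption after a clinician-imposed hold. The text does not support that. NOTE 1 concerns a participant who wishes to start or restart, and holds have their own release conditions in Sections 6.7 and 6.9.

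**Conclusion.** The point holds as an internal contradiction in a rule on who may be given study drug. It is confined to restarts within 60 days of the last dose. Taken literally, NOTE 1 refuses new supply to these men; on the lenient reading it adds repeat Screening tests that Section 5 does not require.

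A reader might go further and conclude that no restart between day 30 and day 60 can occur at a site following NOTE 1, and then calculate a bias in the pooled restart curve. The protocol does not support this. Men can resume with tablets they already hold, and the stopping rate, the share of restarts needing new supply and the number of sites following NOTE 1 are all unknown. An effect on the Section 7.3.1 time-to-restart curve is possible, but its size cannot be derived from the protocol.

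The initiation and adherence rates, and the confidence intervals in Section 7.2, are unaffected. The conclusion rests on the wording of the notes and, for Steps 2 and 3, on nominal visit timing.

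**What to change.** Two wording changes:

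1. In Appendix IA, NOTE 1, after *any participant*, insert *who has not taken PrEP in the past 60 days*. NOTE 1 then has the same scope as Section 5, and the Section 3.2 item can no longer be failed because of study drug.
2. In the Section 5.4 note, add *or restart* after *start*, so that it matches 5.5 and 5.6.

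The cost is a short clarification. If issued as an amendment, it needs the approvals listed in Section 10.5, including the IRBs/ECs and the DAIDS Regulatory Support Center. It adds no visits or tests and may avoid some repeat testing.

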12.0 APPENDIX IB - ADDITIONAL PROCEDURES FOR PARTICIPANTS WITH CONFIRMED HIV INFECTION

	Time of diagnosis (confirmatory visit)	Weeks 4, 8, 13, 26, 39, and 52 (if after HIV diagnosis)	Every 12 weeks after Week 52 ¹
Behavioral Risk Assessment (ACASI)	Х	x ²	х
CD4 cell count testing	Х	Х	Х
HIV viral load testing	Х	Х	Х
HIV genotyping ³	Х		
Additional plasma storage for HPTN NL testing ^{4,5}	Х	Х	Х
Lysed PBMCs for Pharmacology testing ⁶	Х		

¹ Participants with confirmed HIV infection will continue in the study, off of study drug. Any participants who acquire HIV infection during the study will permanently discontinue study product and will be followed after Enrollment at regular visits until the last HIV-uninfected participant reaches Week 52 at that site.

² Excluding Weeks 4 and 8

³ HIV genotyping will be performed in real-time at a laboratory that is used for clinical care at the study site; these results will be provided to the study site and participant. Additional resistance assessments/testing may be performed retrospectively using stored samples shipped to the HPTN NL; those results will not be reported back to study sites or participants.

⁴ In addition to plasma stored at other scheduled visits, additional plasma aliquots must be stored at the time of HIV diagnosis (confirmatory visit) and other visits indicated in Appendix IB. Stored plasma samples from HIV seroconverters will be shipped to the HPTN NL; sites should store samples until they receive a request for shipping from the SDMC. These samples may be used for HIV diagnostic testing, QA testing, Pharmacology testing, resistance testing, and other testing (see footnote 5).

⁵ Additional testing may be performed at the HPTN NL. At the discretion of the HPTN NL, this testing may be performed at another laboratory (e.g., at one of the study sites, at the U.S., CDC, or at another laboratory with special expertise). Results of this testing will not be returned to study sites or study participants. This testing may include additional HIV genotyping/sequencing assays, HIV phenotyping, HIV subtyping, minority variants assays, other assays to characterize HIV viruses and/or the host response to HIV infection.

⁶ If the time of HIV diagnosis (confirmatory visit) occurs at a visit where lysed PBMCs are not already being collected, they should also be collected at this visit for any participant who reports that he used PrEP within 60 days of the confirmatory visit.

